10.3 Handling of Missing Data

This is a prospective pilot study and therefore we do not anticipate any missing data. In the event of any unexpected missing data, no attempt to impute this missing data will be made; missing data will simply be treated as missing in the statistical analysis, and replacement participants will be enrolled to achieve the target accrual of n=50 participants.

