6.5 Secondary Study Endpoints

The secondary endpoint is the incidence of postoperative residual weakness at the time of extubation.

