9.2 Visit 2 (Treatment – day of surgery)

- Elective surgical procedure as per standard of care
- Anesthetic management will be at the discretion of the attending anesthesiologist as per standard of care practice.
- Prior to induction of anesthesia, Tetragraph electrodes will be placed over the ulnar nerve and the thumb and/or pinky finger to measure the response of adductor digit minimi nerve (location of Tetragraph will be at a discretion of the anesthesiologist).
- Following induction of anesthesia but prior to NMBA administration, baseline values will be recorded after calibration.
- Cardiac output will be measured continuously through the pulmonary artery catheter and the values will be obtained from EHR.
- Near the conclusion of the operation but prior to the reversal of NMBA, a set of measurements will be taken
- After sugammadex administration, measurements will be taken every 20 seconds until consecutive measurements demonstrate a TOFR ≥ 0.9 (adequate recovery)
- Each neurostimulation with the TetraGraph will be conducted simultaneously with one observer.
- Time to recovery following SGX (TOFR ≥ 0.9) will be documented as well as time to extubation.
- Following measurements obtained the device will be removed and the patient will proceed along the standard recovery pathway.

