10.2 Statistical Methods

Continuous variables will be summarized as mean (standard deviation) or median (range) while categorical variables will be reported as frequency (percentage). Pearson correlation or Spearman correlation will be used to test 1) the correlation between cardiac output and the time of recovery after reversal with sugammadex and 2) the correlation between age and the time of recovery. Linear regression model will be used to estimate the change of recovery time per unit change in cardiac output or age. If time to recovery does not follow a normal distribution, log transformation will be performed before analysis. All test are two-sided with alpha level set of 0.05 for statistical significance.

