10.4 Subject Population(s) for Analysis

Each participant who goes through the surgery and completes monitoring of residual neuromuscular blockade will be included in the primary analysis regardless of study withdrawal

for any reason. In the event of any study withdrawals, in secondary analysis we will examine the sensitivity of our results to the exclusion of patients who withdrew.

11 Safety and Adverse Events

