11.1.4 Adverse Event Reporting Period

For this study, the follow-up period is defined as up to 10 minutes after arrival to PACU or TOF ratio is > 0.9 (whichever occurs first).

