12.3 Case Report Forms

All data necessary for this study will be obtained from EHR or at the time devices are being used and recorded on the electronic Case Report Forms (CRFs) created in REDCap. All missing data will be explained.

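### If readings stop after sugammadex but before a confirmed TOFR ≥ 0.9, omitting and replacing that patient selects on the primary outcome and can distort the slope and correlation

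*Combined protocol and SAP*

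**What the plan says.** All references are to the combined protocol and SAP.

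- Section 10.3 expects no missing data and rules out imputation. For any missing value it states: "missing data will simply be treated as missing in the statistical analysis, and replacement participants will be enrolled to achieve the target accrual". The reason for the gap plays no part.
- Section 10.4: "Each participant who goes through the surgery and completes monitoring of residual neuromuscular blockade will be included in the primary analysis". Completion is not defined. The only sensitivity analysis there concerns patients who withdrew.
- Section 10.2 plans a Pearson or Spearman correlation. For effect size it says: "Linear regression model will be used to estimate the change of recovery time per unit change in cardiac output or age". A log transformation is allowed, but no method for censored times is named.
- Section 9.2, on the readings: "measurements will be taken every 20 seconds until consecutive measurements demonstrate a TOFR" of at least 0.9. No time cap is given. On care in general: "Anesthetic management will be at the discretion of the attending anesthesiologist as per standard of care practice". No rule ties extubation to the TOFR.
- Section 6.5 makes the "incidence of postoperative residual weakness at the time of extubation" the secondary endpoint. Section 11.1.4 sets the adverse event period as "up to 10 minutes after arrival to PACU or TOF ratio is > 0.9 (whichever occurs first").
- Section 12.3: "All missing data will be explained". No analysis rule uses the explanation.

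**The concern.** The variable at risk of being missing is the primary outcome itself. A patient whose readings end before 0.9 is confirmed is not an empty record: the recovery time is longer than the last reading. Section 10.3 would treat that patient like one with no data. The replacement restores n = 50 but does not bring back the slow recovery, because a replacement counts only if recovery was observed.

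At stake is the size of the reported cardiac output and age slopes and of the correlations. The direction of the error depends on how the end of monitoring relates to cardiac output, and the completed times alone cannot reveal that.

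**Working it through.** **Inputs.** n = 50, correlation 0.6 and power above 90% (section 10.1); two-sided alpha 0.05 (section 10.2). Assumed, because the documents do not give them: a negative sign for the correlation, bivariate normality on the analysis scale, and a loss of q = 2, 5 or 10% (2% is one patient in 50).

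**The plan's own figure.** By Fisher's z, power = Φ(atanh(0.6) × √47 − 1.96) = Φ(0.6931 × 6.856 − 1.96) = Φ(2.79) = 99.7%. The stated figure is met.

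**Case A: the slowest share q is lost.** With ρ = -0.6, let c = Φ⁻¹(1 − q), λ = φ(c)/(1 − q) and v = 1 − cλ − λ², the variance of the remaining recovery times. Then

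- slope = ρv / (1 − ρ² + ρ²v)
- r = ρ√v / √(1 − ρ² + ρ²v)

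At q = 5%: c = 1.645, λ = 0.1086, v = 0.8096. The slope is -0.4858 / (0.64 + 0.36 × 0.8096) = -0.4858 / 0.9315 = -0.52, or 87% of the true -0.60. The correlation is -0.4858 / √(0.9315 × 0.8096) = -0.56.

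**Cases B to D: a variable end of monitoring.** The end time is m − k × CO + e, with CO standardized and e normal with SD 1. A patient is lost if recovery falls after it, and m is set to give q. B has k = 0 (unrelated to CO), C has k = 0.6 and D has k = 0.9 (monitoring longer when CO is low). Simulated with 1,000,000 pairs.

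| Loss mechanism | Slope error at 2 / 5 / 10% | r at 2 / 5 / 10% |
|---|---|---|
| A. Slowest lost | 7 / 13 / 21% too small | -0.58 / -0.56 / -0.53 |
| B. End unrelated to CO | 3–4 / 6 / 10% too small | -0.59 / -0.58 / -0.57 |
| C. Longer in low CO | none | -0.61 to -0.62 |
| D. Longer still in low CO | 2 / 3 / 5% too large | -0.61 / -0.63 / -0.64 |
| E. All readings lost at random | none | -0.60 |

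In C the slope is unbiased because, with k equal to 0.6, being lost depends only on the residual and not on CO. The residual spread shrinks, so r grows slightly.

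**Power.** In case A power at a true r of -0.6 is still at least 98% at 10% lost.

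**Scale against sampling error.** The standard error of r at n = 50 is about (1 − 0.36)/√49 = 0.09. At 2–5% lost, the largest shift in r is 0.02–0.04.

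**The alternative.** Censored normal maximum likelihood returned a slope and an implied correlation of -0.60 in each of cases A to D. In 1,500 simulated trials of n = 50 under case A, the mean slope at 2 / 5 / 10% was -0.61 / -0.60 / -0.60 (SD 0.12) with censoring, against -0.56 / -0.52 / -0.47 (SD 0.11) with omission and replacement. In one uncensored sample of 50, both methods gave slope -0.637 and r -0.613.

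**The case against.** The strongest objection is that the trigger is not shown. Section 9.2 runs readings to confirmed recovery without a cap, so a site that follows it observes every time. Residual weakness at extubation could have zero incidence, and extubation does not itself end the readings. Section 11.1.4 defines a safety reporting period, not a measurement period. Discretion over anesthesia does not override the study's measurement rule. All of this stands: these sections leave room for early stops but do not predict them.

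It is also fair that the effect is small at low rates. At 2–5% lost, r moves by less than one standard error, and nothing in the documents supports a rate as high as 10%. A patient followed to extubation without reaching 0.9 might even be read as having completed monitoring. But that patient still has no recovery time for the planned regression, and section 10.3 then applies.

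Three stronger readings are tempting, and the documents do not support them:

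- A reader might infer that the form in section 18.2, whose timed rows end at +300 sec, imposes a fixed cutoff. It is a form layout; no section makes it a stopping rule.
- A reader might infer that the bias always shrinks the association. Cases C and D show that it can vanish or reverse.
- A reader might infer that the sample size fails. It does not at the planned correlation.

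One might also argue that device failures are harmless and only clinical stops matter. That holds only when the whole record is lost for reasons unrelated to recovery (case E). A failure partway after sugammadex, at a time unrelated to the patient, is case B: slower patients are still more likely to be lost. The useful division is between some usable post-sugammadex readings and none.

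**Conclusion.** The point holds in conditional form. Sections 10.3 and 10.4 state one rule, and for a recovery time known only to exceed the last reading that rule selects on the primary outcome. With a true correlation of -0.6, bivariate normality and 2–10% lost, the slope error runs from 21% too small to 5% too large, depending on how monitoring ends. If no time is incomplete, there is no error at all. The documents do not show that early stops will occur or how often. This is an estimation issue, not a fatal flaw, but it is worth settling before the data are seen, because a rule chosen afterwards could influence the result.

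**What to change.** In sections 10.3 and 10.4:

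1. State that any patient with at least one usable post-sugammadex reading but no confirmed TOFR ≥ 0.9 stays in the primary set, whatever the reason readings stopped. The patient is right-censored at the last reading and is not replaced.
2. Limit omission and replacement to patients with no usable post-sugammadex TOF readings or no cardiac output data.
3. If any time is censored, estimate the slope by censored normal regression, on the log scale if section 10.2 calls for it. Report the correlation implied by that model, b·s/√(b²s² + σ²), where b is the slope, s the SD of the predictor and σ the residual SD (s and σ both with divisor n). With nobody censored, these equal the planned slope and Pearson r.
4. Report the completed-times-only result, including Spearman if used, as a sensitivity analysis. Add the number of incomplete times by reason, from the explanations that section 12.3 already requires. State the assumption that the end of monitoring is not informative given cardiac output.

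The cost is a few sentences, one standard regression routine, slightly more analysis work and one assumption that cannot be tested. No extra patients are needed.

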10.4 Subject Population(s) for Analysis

Each participant who goes through the surgery and completes monitoring of residual neuromuscular blockade will be included in the primary analysis regardless of study withdrawal

for any reason. In the event of any study withdrawals, in secondary analysis we will examine the sensitivity of our results to the exclusion of patients who withdrew.

11 Safety and Adverse Events

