4.3 Risks and Benefits

- The benefits of using neuromuscular blockade monitoring devices:
Early detection of optimal time for tracheal intubation; optimal management of intraoperative depth of neuromuscular block to facilitate surgical procedures; determination of appropriate time and dose of sugammadex reversal; and detection of residual neuromuscular blockade
- The risks of using neuromuscular blockade monitoring devices:
Slight discomfort when electrical stimulation is administered in awake volunteers; however, our patients will be anesthetized, rendering this risk as extremely minor.

5 Study Objectives

Primary Objective

To determine the recovery time from rocuronium-induced blockade after reversal with sugammadex as a function of cardiac output.

Secondary Objective

To determine the correlation between the speed of recovery from NMBA with sugammadex and age.

6 Study Design

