7.1 Inclusion Criteria

- Age > or = 18 years old
- Patients willing to participate and provide an informed consent
- Patients undergoing an elective surgical procedure requiring administration of rocuronium, and the use of a pulmonary artery catheter intraoperatively.

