18.2 Intraoperative Data

Study ID:	Date of Surgery (dd / mm / yyyy):		Examiner's Initials:
Wrist circumference (right):	Wrist circumference (left):		
Age (yrs):	Weight (kg):	Height (cm):	BMI:
Muscle relaxant name:			
Muscle relaxant total dose (mg):			
Time of first muscle relaxant dose (mm : hh):		: am / pm	
Time of last muscle relaxant dose (mm : hh):		: am / pm	
Sugammadex dose (mg):			
Time of Sugammadex administration (mm : hh):		: am / pm	

Time of extubation:	:	am / pm
---------------------	---	---------

TetraGraph (TG)

Arm tested: dominant / non-dominant

	Time	TOFC # 1	TOFC # 2	TOFC # 3	CO
		TOFR # 1	TOFR # 2	TOFR # 3	
Calibrated baseline and supramax current					
TOFC=0 (after initial NMBA dose)					
pre-SGX					
+20 sec			N/A	N/A	
+40 sec			N/A	N/A	
+60 sec			N/A	N/A	
+80 sec			N/A	N/A	
+100 sec			N/A	N/A	
+120 sec			N/A	N/A	
+140 sec			N/A	N/A	
+160 sec			N/A	N/A	

+180 sec			N/A	N/A	
+200 sec			N/A	N/A	
+220 sec			N/A	N/A	
+240 sec			N/A	N/A	
+260 sec			N/A	N/A	
+280 sec			N/A	N/A	
+300 sec			N/A	N/A	
Extubation			N/A	N/A	
Time to recovery following SGX (TOFR ≥ 0.9) (two consecutive measurements)					

19 List of In-Text Figures

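### The primary analysis attaches no condition to the pre-sugammadex reading, so a participant who has already recovered would enter with a floor time that says nothing about reversal

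*Combined protocol and SAP*

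**What the plan says.** The primary objective (Section 5) is: "To determine the recovery time from rocuronium-induced blockade after reversal with sugammadex as a function of cardiac output". It presumes a block but sets no condition on one.

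- **Eligibility (7.1)** covers: "Patients undergoing an elective surgical procedure requiring administration of rocuronium, and the use of a pulmonary artery catheter intraoperatively".
- **Conduct (9.2)** does not standardise depth of block or timing of reversal: "Anesthetic management will be at the discretion of the attending anesthesiologist as per standard of care practice".
- **Pre-reversal reading (9.2):** "Near the conclusion of the operation but prior to the reversal of NMBA, a set of measurements will be taken". No threshold or consequence is attached. Form 18.2 has a pre-SGX row with three sets of count and ratio fields. Its row for a count of zero refers only to the time after the initial relaxant dose.
- **Measurement rule (9.2):** "After sugammadex administration, measurements will be taken every 20 seconds until consecutive measurements demonstrate a TOFR ≥ 0.9 (adequate recovery". The first post-sugammadex row on form 18.2 is +20 sec. The summary row reads "Time to recovery following SGX (TOFR ≥ 0.9) (two consecutive measurements" and does not say whether the first or the second of the two readings is the recovery time.
- **Analysis set (10.4):** "Each participant who goes through the surgery and completes monitoring of residual neuromuscular blockade will be included in the primary analysis".
- **Analysis (10.2):** a Pearson or Spearman correlation and a linear regression on cardiac output or age, with log transformation if recovery time is not normal. No term for pre-reversal depth is named.
- **Replacement (10.3)** applies to missing data only.

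**The concern.** Suppose a participant's TOFR is already 0.9 or more at the pre-sugammadex reading and sugammadex is still given. The readings at +20 s and +40 s then meet the stopping rule, and the recorded time is the floor of the form. There was no block left to reverse, so the number reflects the reading grid. It is not missing, so 10.3 does not remove or replace it, and 10.4 keeps it in the primary analysis.

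Two things are at stake. First, dilution: a cluster of constant times weakens both the correlation and the estimated seconds per unit of cardiac output. A larger sample does not cure the slope. Second, bias: the floor value cannot vary with cardiac output, but the chance of having recovered beforehand might, and the slope could then be pulled either way.

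This differs from the general absence of adjustment for depth of block. Where no block remains, there is no reversal time to adjust.

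**Working it through.** **1. The plan's own figure.** Inputs from 10.1 and 10.2: n = 50, r = 0.6, two-sided alpha 0.05. By the Fisher z approximation, power = Φ(atanh(r)·√(n−3) − 1.96). With atanh(0.6) = 0.693 and √47 = 6.856, this is Φ(4.752 − 1.96) = Φ(2.79) = 99.7%. The statement of more than 90% is correct; 25 patients would give 90%.

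**2. Assumptions that are not in the documents.** In blocked patients, mean recovery time is 120 s, SD 40 s and r = −0.6. A share f is already recovered and recorded at a floor of 20 s or 40 s. At first, f is unrelated to cardiac output (CO).

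**3. Slope.** Per SD of CO, the slope in blocked patients is −0.6 × 40 = −24 s. A constant time contributes no covariance, so the mixed slope is (1 − f) × (−24): −22.8, −21.6 and −19.2 s at 5%, 10% and 20%. The shrinkage equals f, for either floor and any n.

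**4. Correlation and power.** r_mixed = r(1 − f)/√[(1 − f) + f(1 − f)d²], where d = (mean − floor)/SD. That is 100/40 = 2.5 for a 20 s floor and 80/40 = 2 for a 40 s floor. Example, f = 10%, 20 s floor: 0.6 × 0.9/√(0.9 + 0.09 × 6.25) = 0.54/1.209 = 0.447. Power is from simulated trials of 50 on the raw scale, because the mixture is not normal; Fisher z gives figures up to about 2 points higher.

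| Share | r, 20 s floor | Power | r, 40 s floor | Power |
|---|---|---|---|---|
| 5% | −0.51 | 96% | −0.53 | 98% |
| 10% | −0.45 | 89% | −0.48 | 94% |
| 20% | −0.36 | 72% | −0.40 | 81–82% |

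**5. Sensitivity to the SD.** With SD 50 s, a 20 s floor and f = 10%, d = 2, the same as SD 40 s with a 40 s floor, so power is again about 94%.

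**6. Log scale.** On the log scale the floor values lie further out. With a 10% share and a 20 s floor, simulated power is roughly 50% to 60%, depending on the SD and shape assumed for blocked patients. With a 40 s floor it is roughly 73% to 84%. Spearman power at a 20% share and 20 s floor is about 74% to 77%, so ranking does not remove the loss.

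**7. If prior recovery is related to CO.** Let recovered patients' CO differ by δ SD. Slope = [(1 − f)(−24) + f(1 − f)δ(floor − mean)]/[1 + f(1 − f)δ²]. With f = 10% and a 20 s floor:
- δ = −1: (−21.6 + 9)/1.09 = −11.6, a ratio of 0.48 to the true slope. The SD of times is √(0.9 × 1600 + 0.09 × 10000) = 48.4, so r = −12.6/(48.4 × 1.044) = −0.25.
- δ = +1: (−21.6 − 9)/1.09 = −28.1, a ratio of 1.17.

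**8. Power after restriction.** At r = 0.6, Fisher z power is 99.4% with 45 patients, 98.8% with 40, 97.5% with 35 and 95.0% with 30.

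**The case against.** The strongest reply is that the case may hardly arise. Section 4.3 lists guidance on the time and dose of reversal among the benefits of monitoring. Section 8.3 says there is no masking (8.2 says single-blinded), and neither section says the reading is hidden from the team. Nothing in 9.2 obliges sugammadex in a recovered patient. A share near zero fits the documents as well as 20% does. This stands, and it limits what can be said about size.

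A reader might infer more than the documents support on three counts:
- **That the recorded time is certainly 20 s.** Form 18.2 does not say which of the two consecutive readings counts, and no text says what to record when the pre-sugammadex row already meets 0.9. An analyst could even treat such a case as having no recovery time. The plan is silent on this.
- **That power falls below the stated 90% once 10% have recovered.** The 89% needs the raw scale, SD 40 s and a 20 s floor together. With SD 50 s or a 40 s floor it is about 94%.
- **That 7.1 and 7.2 are at fault.** Screening criteria cannot use an intraoperative reading. The place for the rule is 10.4.

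Two objections concern the remedy. A participant at 0.85 may also reach 0.9 by the first reading and would stay in, so a cut at 0.9 does not clear the near-floor region. And the pre-sugammadex set has three readings, timed only as near the end of the operation, so a rule must name one, and some participants may still recover between that reading and the injection. Both stand as limits. If prior recovery depends on cardiac output, the restriction also changes the mix of cardiac output in the analysed set. That matches the question, which concerns patients with a block, but it is a reason to show the all-participant result too.

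**Conclusion.** The gap is real. Followed as written, 10.4 puts already-recovered participants in the primary analysis with a constant time that carries no information about reversal of a block. The slope shrinks by exactly their share if prior recovery is unrelated to cardiac output, and is biased in either direction if it is related. The effect on power depends on the share, the SD, the floor and the scale. None of the first three is settled in the documents, and 10.2 leaves the last to the data. The figures above are therefore illustrations, not predictions.

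The documents do not show that many such participants will occur, and the sample size statement in 10.1 is not wrong. The change is worth making because it is cheap, uses a reading already collected, and settles the question before recovery times are seen.

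**What to change.** In 10.4, limit the primary analysis to participants whose last TetraGraph reading before sugammadex shows TOFR below 0.9, or a train-of-four count below 4. Report how many had already recovered, list them separately with their cardiac output, and keep the analysis of all monitored participants as a sensitivity analysis. State on form 18.2 which of the two consecutive readings is the recovery time, so that the floor is defined.

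The cost is about one sentence in 10.4 and a label on the form, with no new data and no change to care. The rule uses a reading taken before the outcome. Replacement is unnecessary: at r = 0.6, power is still about 99% with 40 patients and 95% with 30. The downsides are a slightly smaller primary analysis set, and that participants just below 0.9 remain near the floor.
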